A third study was conducted in 10 subjects to investigate using the introduction of BSS following Zepto™ capsulotomy as a means to separate the capsule button off the roof of the suction cup, and at the same time float off the suction cup from the capsule. In addition, the last 5 subjects received a slightly longer duration of suction to create apposition of the nitinol ring against the capsule. In these 5 cases, suction was maintained until the surgeon verified visually that small bubbles in the OVD ceased movement, indicating full suction. All 10 subjects that received Zepto™ capsulotomies had complete capsulotomies with a capsule button separated

from the suction cup and remaining in the anterior chamber. All underwent successful phacoemulsification with intracapsular IOL fixation. Eight out of the 10 subjects returned for follow up at 4 weeks. There were no adverse clinical findings and no capsule related problems. All 10 Zepto™ capsulotomies were successful, and visual confirmation of full suction provided assurance of capsulotomy completion.

A fourth study of 10 subjects was undertaken to re-confirm the effectiveness of the BSS float-off mechanism to separate the capsule button from the suction cup and to float-off the suction cup from the capsule. In all cases, the surgeon was also instructed to wait for visual confirmation of cessation in OVD movement prior to initiating Zepto™ capsulotomy. All 10 Zepto™ capsulotomies resulted in complete round capsule openings with no residual tissue bridges. All 10 capsule buttons were free floating and easily identified and retrieved by the surgeon. All 10 subjects underwent successful phacoemulsification with intracapsular IOL fixation.

V. STUDY OBJECTIVE

This study will evaluate outcome in subjects who have elected to have Zepto™ capsulotomies during cataract surgery with phacoemulsification.

VI. PARAMETERS

A. Primary Effectiveness Endpoint - Complete Capsulotomy (At least 95% of cases)

Clinical Discussion - In clinical practice, a successful capsulotomy results in a rounded, anterior capsular opening through which the cataract can be extracted. The capsulotomy preserves a bag-like configuration of the remaining lens capsule, which enables secure intracapsular fixation of the IOL.

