A successful complete Zepto™ capsulotomy is defined in this protocol to be one that results in a complete 360° capsulotomy without any residual tissue bridges visible to the surgeon. If there are such tissue bridges, the surgeon completes the capsulotomy manually.

Effectiveness Rate – An effectiveness rate of 95% complete capsulotomies provides reasonable assurance that the Zepto™ system is effective.

Data Recording - The presence of a complete capsulotomy without tissue bridges will be recorded by the surgeon as a Yes or No following each Zepto™ capsulotomy.

B. Primary Safety Endpoint - Posterior Capsular Rupture & Vitreous Loss (4% or less)

Clinical Discussion - Posterior capsular rupture & vitreous loss is generally considered one of the most significant complications of cataract surgery that occurs with some frequency. One well recognized cause is posterior extension of an anterior capsular radial tear. It is noteworthy however, that the majority of anterior capsular tears do not

adversely impact visual outcome.³ Posterior capsular rupture and vitreous loss subject the patient to additional risks of postoperative complications commonly resulting in suboptimal best corrected visual acuity, and usually precludes intracapsular IOL fixation. Due to its potential adverse impact on best corrected visual acuity, posterior capsular rupture and vitreous loss related to Zepto™ capsulotomy is chosen as the primary safety endpoint.

Posterior Capsule Rupture & Vitreous Loss Rate – The incidence of posterior capsular rupture and vitreous loss has been documented in 13 peer-reviewed publications over the period between 1999-2011. With one exception, all of these studies have shown rates ranging from 1.1 to 4.4 percent depending on surgeon group ⁴⁻¹⁶. A posterior capsular rupture and vitreous loss rate within the range of this published data in subjects receiving Zepto™ capsulotomies will provide reasonable assurance that the Zepto™ capsulotomy system acceptably meets the safety endpoint in the proposed study.

Data Recording – The occurrence of a posterior capsular rupture and vitreous loss will be recorded by the surgeon as a Yes or No following the completion of surgery.

C. Other Parameters To Be Captured

- 1) Anterior Capsule Tear – The occurrence of an anterior capsule tear will be recorded by the surgeon as a Yes or No after the completion of Zepto™ capsulotomy.

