Only subjects discontinued prior to Zepto™ capsulotomy may be replaced in the study. Those subjects who are enrolled to replace withdrawn subjects will receive new ID numbers.

B. CLINICAL PARAMETERS

The following list of clinical parameters is typically collected as part of routine pre-operative testing. If they are not collected as part of the routine pre-operative examination, they will be collected as study specific procedures prior to cataract surgery.

1. Manifest refraction
2. Uncorrected distance visual acuity (UCVA)
3. Best spectacle corrected distance visual acuity (BSCVA)
4. Dilated pupil size
5. Slit lamp and fundus examination

[figure not shown]
C. EXAMINATION SCHEDULE

Subjects enrolled in the study will be required to commit to the following examination schedule and take part in the clinical evaluations as outlined in Appendix 2.

Preoperative Evaluation	(Day -14 to Day -1)
Operative Evaluation	(Day 0)
Day 1	(1 to 2 days postoperative)
Week 1	(5 to 12 days postoperative)
Month 1	(3 to 6 weeks postoperative)

D. DESCRIPTION OF DEVICE

The Mynosys Zepto™ System consists of a disposable surgical handpiece (104mm x 22mm (4.14" x 0.866") that is operated by the surgeon to perform the capsulotomy and which is connected to a small table-top control console (10" w x 14" d x 7" h) located within the surgical suite (see Figure 1). In use, the surgeon holds the device in a horizontal grip. The functional portion used for capsulotomy is the capsulotomy tip located at the front end of the handpiece and consists of a circular, soft silicone suction cup 1.18 mm in height and 6.10 mm in diameter. This silicone suction cup houses a nitinol ring that delivers the energy pulses to create the capsulotomy. The capsulotomy handpiece is connected to the console containing suction controls, electronic timing circuits, safety diagnostics, and an audio interface.

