A Zepto™ capsulotomy is performed by applying suction to the suction cup causing the nitinol ring to be apposed to the lens capsule. A series of 12 electrical pulses lasting a total of 4 milliseconds is delivered to the nitinol ring causing rapid phase transition of water molecules trapped between the bottom edge of the nitinol ring and the capsule. The rapid volume expansion results in the capsule cutting action. Suction is then vented to atmosphere. The operating assistant will, upon command from the physician, introduce a small amount of Balanced Salt Solution (BSS) into the suction cup to allow for a gentle release of the suction cup from the capsule, and to allow the free-floating capsule button to stay behind in the anterior chamber for manual removal with forceps. Upon completion of the capsulotomy, the disposable Zepto™ Handpiece tip is removed from the eye.

E. ZEPTO™ CAPSULOTOMY PROCEDURE

The Zepto™ capsulotomy will be performed on Day 0 of the study according to the following instructions:

1. Patient Preparation
 - 1.1. Obtain preoperative dilation per standard protocol.
 - 1.2. Obtain anaesthesia per standard protocol.
 - 1.3. Clean the subject's eyelids and ocular adnexa with disinfecting solution.
 - 1.4. Apply sterile drapes.
2. Zepto™ System Setup
 - 2.1. Ensure that the red 'Emergency Off' button is in the 'Out' position.
 - 2.2. Plug the female end of the Zepto™ Power Cord into the rear of the Zepto™ Power Console, and then plug the male end of the power cord into a properly grounded electrical outlet.
 - 2.3. Make sure the area around the electrical outlet is clear and easily accessible, in case there is a need to unplug the Zepto™ Power Console from the outlet.
 - 2.4. Make sure that the electrical outlet that you use is not controlled by a light switch, and do not use an extension cord that has a switch. The Zepto™ Power Console must remain powered on at all times to work properly.
 - 2.5. Turn on power for the Zepto™ Power Console using the small switch located on the rear power entry module where the power cord plugs in. The Zepto™ Power Console will perform a self-check. A successful Zepto™ Power Console self-check will result in a flashing green Status light.
 - 2.6. Open the package, and pass the Fluid Isolator to the operating attendant.
 - 2.7. Aseptically remove the Mynosys disposable Zepto™ Handpiece from the outer pouch and aseptically transfer the inner pouch to the scrub nurse.

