 - 2.8. Remove the Fluid Isolator from the pouch.
 - 2.9. After retrieving the Zepto™ Handpiece from the inner pouch in a sterile manner, connect the disposable Zepto™ Handpiece suction line to the Fluid Isolator.
 - 2.10. Connect the 10cc syringe to the Fluid Isolator.
 - 2.11. Connect the Fluid Isolator to the Luer-Lok connector at the front of the Zepto™ Power Console.
 - 2.12. Connect the electrical cable to the 5 pin receptacle at the front panel of the Zepto™ Power Console.
 - 2.13. After the Zepto™ Handpiece self-check is successfully completed, the flashing green light will convert to a constant ON green light, indicating the system is ready.
 - 2.14. Pull the protective tip cover off the end of the disposable Zepto™ Handpiece, being careful not to damage the Zepto™ tip.

3. Surgical Procedure

- 3.1. Create a clear corneal incision of 2.2mm or greater.
- 3.2. Use an Ophthalmic Viscosurgical Device to stabilize the anterior chamber.
- 3.3. Submerge Zepto™ capsulotomy tip into sterile Balanced Salt Solution (BSS).
- 3.4. Pull the syringe plunger to the end of travel.
- 3.5. Slide the finger slider distally on the disposable Zepto™ Handpiece to elongate the Zepto™ capsulotomy tip for insertion into the corneal incision (Do not pull back on the finger slider until the Zepto™ capsulotomy tip has been inserted completely into the anterior chamber).
- 3.6. Stabilize the eye with a Thornton fixation ring, and insert the Zepto™ capsulotomy tip through the corneal incision.
- 3.7. Once the Zepto™ capsulotomy tip is fully within the anterior chamber, slide the finger slider proximally to return the capsulotomy tip to a circular state.
- 3.8. Position the Zepto™ capsulotomy tip on the capsular bag, centering the device using the desired centration method.
- 3.9. Instruct assistant to press the “Suction” button on the console to initiate suction cup and nitinol ring apposition onto the lens capsule.
- 3.10. Visually confirm the flow of OVD has stopped by monitoring the movement of bubbles in the OVD. When the OVD ceases to flow, full suction has been achieved.
- 3.11. Instruct assistant to press the “Cut/Release” button on the console to perform the capsulotomy (once capsulotomy energy is delivered, the suction is automatically vented to atmosphere).

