- 3.12. Instruct assistant to introduce small amount of pre-loaded BSS into the suction cup to gently release the suction cup from the capsule (this is done by the assistant moving a roller clamp on the suction tubing).
- 3.13. Stabilizing the eye with the Thornton fixation ring, remove the Zepto™ Handpiece capsulotomy tip from the anterior chamber by manually withdrawing it through the corneal incision. The Zepto™ capsulotomy tip automatically folds and conforms to the incision as it is withdrawn from the eye.
- 3.14. The excised capsule “button” (circular piece of capsule tissue that has been cut) from the capsulotomy will be free-floating within the anterior chamber and can be retrieved by forceps.
- 3.15. In the event of an incomplete capsulotomy with remaining tissue bridges, use the manual Continuous Curvilinear Capsulorhexis technique to complete the capsulotomy.

F. POSTOPERATIVE CARE

The subject will be instructed by the operating physician on normal post-op cataract surgery instructions.

G. DATA REPORTING

A Case Report Form (CRF) binder will be used for each subject enrolled in the study. The appropriate CRF, provided under separate cover in a binder specific to this study, will be completed and signed by the investigator after each examination. All CRFs will be completed in a legible manner in ink. Any corrections will be made by drawing a single line through the incorrect entry, entering the correct information, and initialing and dating the change.

H. STUDY COMPLETION PROCEDURES

Subject Completion: Subjects are considered to have completed the study if they have completed all follow-up examinations through month 1.

Subject Termination: Subjects may be terminated from the study at the discretion of the Principle Investigator only for reasons related to the study regimen that would jeopardize the subjects' health and/or welfare if they were to continue in the study. However, every effort will be made to follow terminated subjects for safety reasons using the appropriate case report forms until the planned end of the study period.

Subjects Discontinuation/ Lost to Follow-up: Subjects may be discontinued from the study for non-study-related reasons only when no other option is possible. Reasons for discontinuation include, but are not necessarily limited to:

- 1) Voluntary withdrawal from the study by the subject;
- 2) Subject has moved from the area and is determined to be lost to follow-up;

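### Could an eye in which the Zepto tip is inserted but no cut is made drop out of the effectiveness rate?

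*Protocol*

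**What the plan says.** Section VI.A defines success as a "complete 360° capsulotomy without any residual tissue bridges visible to the surgeon" and sets the recording rule: "The presence of a complete capsulotomy without tissue bridges will be recorded by the surgeon as a Yes or No following each Zepto™ capsulotomy". The replacement rule, given in IX.A and repeated in IX.H, is that "Only subjects discontinued prior to Zepto™ capsulotomy may be replaced in the study".

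The term on which both rules depend is used in three ways:

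- **Whole procedure.** Section IX.E is headed as the Zepto capsulotomy procedure. It says the capsulotomy is done on Day 0 according to instructions that run from patient preparation, through tip insertion (step 3.6), suction (3.9 to 3.10) and cutting (3.11), to manual completion where tissue bridges remain (3.15).
- **Suction onward.** Section IX.D: "A Zepto™ capsulotomy is performed by applying suction to the suction cup".
- **The cut.** In step 3.11 the assistant presses a "button on the console to perform the capsulotomy". The account of the fourth earlier study in section IV has the same sense: surgeons were to "wait for visual confirmation of cessation in OVD movement prior to initiating Zepto™ capsulotomy".

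On leaving the study, IX.H says: "Subjects may be discontinued from the study for non-study-related reasons only when no other option is possible". It deals separately with termination for reasons tied to the study regimen.

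**The concern.** Tip insertion comes five steps before the cut. Suppose the tip is in the eye but full suction is never reached, or no energy is delivered. If the capsulotomy is the cut alone, that eye has not had one. Nothing then triggers the Yes/No entry, and the subject might be regarded as still eligible for replacement. Step 3.15 does not help, because it covers only bridges left after a cut.

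The direction of the error is what makes this worth checking. Section XII rules out hypothesis testing and rests the evaluation on point estimates and exact intervals, read against the 95% in VI.A. Leaving out an eye in which the device failed can only raise the rate. With 100 eyes and a target of 95%, one or two eyes could decide on which side of the mark the estimate falls.

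**Working it through.** **Reproducing the plan's figure.** Inputs from sections XI and XII: n = 100, x = 95, Clopper-Pearson, two-sided 95%. The lower limit is the 0.025 quantile of Beta(x, n − x + 1) and the upper limit is the 0.975 quantile of Beta(x + 1, n − x). The result is 88.72% to 98.36%, as printed in XI.A.

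**Size if uncut eyes were left out.** The protocol gives no rate for such eyes, so their number k is an assumption.

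*Replaced.* With 95 complete, 5 bridged and k uncut eyes replaced, the report stays at 95/100. Counting the uncut eyes as failures gives 95/(100 + k):

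| k | Rate | Exact 95% interval |
|---|---|---|
| 0 | 95/100 = 95.00% | 88.72 to 98.36 |
| 1 | 95/101 = 94.06% | 87.52 to 97.79 |
| 2 | 95/102 = 93.14% | 86.37 to 97.20 |
| 3 | 95/103 = 92.23% | 85.27 to 96.59 |

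*Unscored, not replaced.* With 94 successes among 100 eyes and two of the six non-successes uncut and left blank, the report is 94/98 = 95.92% (89.88 to 98.88) in place of 94/100 = 94.00% (87.40 to 97.77).

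One omitted eye is therefore worth 95.00 − 94.06 = 0.94 points in the first case and (95.92 − 94.00)/2 = 0.96 in the second. With replacement and an observed 95, 96, 97 or 98 of 100, it takes 1, 2, 3 or 4 omitted eyes to fall below 95%: 95/101 = 94.06%, 96/102 = 94.12%, 97/103 = 94.17%, 98/104 = 94.23%.

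**Likelihood.** Section IV describes 10 + 4 + 10 + 10 = 34 eyes treated with Zepto and no eye entered without a cut. The exact upper limit for 0/34 is 1 − 0.025^(1/34) = 10.28%, so a low rate is not excluded. The four eyes with the suction leak are not examples: they were cut, were left with bridges, and would be scored No here.

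**Whether the text lets such an eye go.** The passages, read together:

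1. *Start point.* IX.E is the operating section of this protocol and includes tip insertion. On its use of the term, an entered eye is within the Zepto capsulotomy, hence due a score and past the point of replacement. The wording in section IV reports what surgeons were told in an earlier study and sets no rule for this one. Step 3.11 is an operating instruction and does not address scoring.
2. *Replacement.* It requires a discontinued subject. IX.H speaks of discontinuation for reasons unrelated to the study and as a last resort; its examples are withdrawal, moving away and non-cooperation. A failed deployment is study-related, and a subject who goes on to cataract surgery by another technique can still be followed to Month 1.
3. *Scoring.* Appendix 2 lists completeness of capsulotomy on Day 0, so a blank would be a missing scheduled item and open to query. An uncut eye cannot satisfy the definition in VI.A, so No is the only entry that fits.
4. *Trace.* Section X.A counts a device that does not work at all as a device failure, and X.D requires a report to the sponsor within 48 hours even when no serious or unanticipated event follows.
5. *Safety endpoint.* Posterior capsular rupture with vitreous loss is recorded after surgery is complete, so it does not depend on where the capsulotomy starts.

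**The case for a change.** The best argument for amending is that recording and replacement are carried out at the site. An SAP can define an analysis set, but it cannot recover an entry never made or undo a replacement. With up to eight sites, surgeons could read a loose term differently. The list of reasons for discontinuation in IX.H is expressly open-ended, and malfunction reports are not linked to the effectiveness record. Anterior capsule tear and corneal touch are also tied to completion of the Zepto capsulotomy, although corneal touch could occur on insertion alone. A clarifying sentence would cost little.

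Part of this stands. No sentence says in terms that an entered but uncut eye is scored No, and the three uses of the term are not reconciled. But the harm needs several things together: an event not described in any of the 34 earlier eyes, a surgeon who sets aside IX.E and leaves a scheduled item blank, and an analyst who drops the eye despite a malfunction report. The last step is an inference, since nothing in the protocol removes an unscored eye from the denominator, and the handling of missing scores is commonly left to the SAP, which is not at hand. Nor is every uncut eye clearly a device failure: an attempt abandoned for a patient-related reason could fairly be classed otherwise.

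**Conclusion.** No change is called for. The protocol leaves the start of the Zepto capsulotomy undefined, but its own procedure section, the Day 0 schedule and the definition of success all lead to the same handling: an eye that is entered but not cut is scored No and is not replaced. Were such eyes omitted, each would raise the reported rate by about 0.9 to 1.0 points near 95%. That is small beside the planned interval of 88.72% to 98.36%, though enough to cross 95% when the estimate sits close to it. If no such eye occurs, nothing changes. The conclusion assumes that sites use the term as IX.E does and complete the scheduled Day 0 item. It also assumes that the analyst treats a blank accompanied by a malfunction report as a failure, not as an eye to be dropped.

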- 2) Corneal Touch - The occurrence of corneal touch by the Zepto™ capsulotomy tip during its use will be recorded by the surgeon as a Yes or No after the completion of Zepto™ capsulotomy.
- 3) Capsulotomy Diameter – The diameter of the Zepto™ capsulotomy will be measured during surgery by the surgeon using an intraocular rhesis ruler.

VII. STUDY DESIGN

This study is a prospective, non-randomized, multi-site clinical study with up to 8 clinical sites enrolling a total of 100 eyes of subjects aged 22 and older, who will have Zepto™ capsulotomy followed by conventional phacoemulsification and IOL implantation.

Subjects will be screened for eligibility and informed consent will be obtained from those who meet screening criteria and are interested in participation in the study. Eligible subjects will be examined preoperatively to obtain a medical history and to establish a baseline for ocular condition. Baseline measurements will be collected as outlined in Section IX.

VIII. SUBJECT POPULATION

Subjects with symptomatic age-related lens cataract desiring lens extraction and IOL implantation.

A. INCLUSION CRITERIA

1. Subjects must be age 22 or older,
2. Subjects consenting to undergoing phacoemulsification and IOL implant surgery for the treatment of symptomatic age related lens cataract, and then electing to undergo Zepto™ capsulotomy,
3. Subjects must be willing and able to return for scheduled treatment and follow-up examinations for 1 month.

B. EXCLUSION CRITERIA

1. Disease or pathology in the treatment eye that will compromise visual performance or refractive outcome (e.g. previous refractive surgery),
2. Zonular abnormality,
3. Posterior polar cataract,
4. Fellow eye with acuity less than 20/200,
5. Any prior ocular surgery of the study eye,
6. Advanced glaucoma (greater than 0.8 cup: disk) or intraocular pressure \geq 30 mmHg in the study eye,
7. Pupillary dilation during the pre-operative exam of less than 7 mm in diameter,
8. Proliferative diabetic retinopathy,
9. Disorders of the ocular muscles, such as nystagmus or strabismus,
10. Chronic uveitis,
11. Abnormal corneal endothelium,
12. Subjects on medications with, in the opinion of the surgeon, significant ocular side effects,
13. Pregnant or nursing (lactating) women,
14. Implanted ocular device or drug in the study eye,

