1. The known or foreseeable risk of adverse events associated with the procedures involved in the research that are described in (a) the protocol related documents, such as the IRB-approved research protocol, any applicable investigator brochure, and the current IRB-approved informed consent document, and (b) other relevant sources of information, such as product labeling and package inserts; or
2. The expected natural progression of any underlying disease, disorder, or condition of the subject(s) experiencing the adverse event and the subject's predisposing risk factor profile for the adverse event.

B. Identification and Collection

Identification and collection of an adverse event begins after informed consent has been obtained and documented. Standard sources for identifying adverse events include:

- Direct observation by the investigator
- Asking the study participant a non-specific question (i.e., "Have you had any problems since the last visit?")
- Unsolicited volunteering of information by the study participant (i.e., "Doctor, I have had numerous headaches since I started using this lens.")
- Subject symptoms/complaints reported via subject questionnaire
- Laboratory or test results that meet protocol requirements for classification as an adverse event (e.g., IOP over 30 mmHg)

The Investigator will review each event, assess its relationship to the Zepto™ system and the severity of the event (see definitions provided below), will determine if the event is serious and if it is unanticipated. In addition, the Investigator will document subsequent treatment/intervention and resolution status for all Adverse Events.

All adverse events and adverse device effects observed or elicited by the investigator, reported by the subject, or resulting from a test result, etc., occurring during the clinical investigation must be documented in the source documentation. All ocular adverse events are transcribed to the Adverse Event CRF. During the study, the investigator should treat the study subject as appropriate to ensure his/her safety and welfare.

Cataract Surgery Adverse Events

Specific to this protocol, pre-existing conditions (including cataract/planned cataract surgery on the non-study eye) will not be considered adverse event/serious adverse events, but will be collected at the preoperative visit. A worsening of a pre-existing condition during the study should be documented as an adverse event and evaluated accordingly.

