Although the following may be considered normal or expected events after cataract surgery, for purposes of this protocol, the following items must be documented as adverse events and evaluated accordingly:

- Anterior capsule tear

- Posterior capsule rupture with or without vitreous loss
- Choroidal effusion hemorrhage
- Corneal edema, corneal decompensation
- Corneal abrasion
- Post-operative uveitis
- Endophthalmitis
- Posterior capsule opacification
- Macular edema
- Retinal tear or retinal detachment
- Elevated intraocular pressure
- Decentered IOL
- Wound leak
- Posterior vitreous detachment
- Medication allergy or intolerance
- Ptosis
- Capsulotomy decentration
- Zonular instability
- Corneal burn
- Corneal endothelial tear
- Anterior capsule fibrosis/anterior capsule contraction syndrome

C. Evaluation

When evaluating adverse events, the investigator must determine if the event is serious, assess the severity of symptoms, the relationship of the event to the study device and study procedure, and whether or not the event was unanticipated using the following guidelines:

1. Severity

- Mild: Subject awareness of a sign or symptom that is easily tolerated, requires no treatment, and does not interfere with subject's daily activities
- Moderate: Subject awareness of a sign or symptom which may be a low level of concern to the subject and may interfere with daily activities, but can be relieved by simple therapeutic care
- Severe: A sign or symptom that interrupts the subject's daily activity and requires systemic therapy or other treatment.

2. Relationship to Study Device or Study Procedures (Causality)

- Probably: Any untoward medical occurrence reported in a subject, user, or other person, which might have a direct relationship to the study device/study protocol, including any malfunction, failure, deterioration in the characteristics or deployment and/or performance of the device, as well as any inadequacy in the labeling or the instructions for use, and an alternative cause is unlikely or significantly less likely compared to the potential

relationship to the study device/study protocol.

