- Possibly: Any untoward medical occurrence reported in a subject, user or other person, which might have a direct or indirect relationship to the study device/study protocol, including any malfunction, failure, deterioration in the characteristics or deployment and/or performance of the device, as well as any inadequacy in the labeling or the instructions for use and an alternative cause is equally or less likely compared to the potential relationship to the study device/study protocol.
- Unlikely: Any untoward medical occurrence reported in a subject, user or other person, which might have a little relationship to the study device/study protocol, including any malfunction, failure, deterioration in the characteristics or deployment and/or performance of the device, as well as any inadequacy in the labeling or the instructions for use and a likely alternative cause exists.
- Unrelated: Any untoward medical occurrence reported in a subject, user or other person, which has no direct or indirect relationship to the study device/study protocol, and a more likely alternative cause (underlying or concurrent illness, effect of another procedure/device/drug) is identified or strongly suspected.

D. Reporting

1. On-Site Serious Adverse Event (SAE) Reporting

The site should report any event to the Sponsor in an expedited manner if it meets the criteria for an SAE, or Serious Adverse Device Effect. Expedited reporting is calling, e-mailing, or faxing the Sponsor within 24 hours of becoming aware of the event. When calling or e-mailing the Sponsor to report an SAE or Serious Adverse Device Effect, the site should forward any supporting documents along with the SAE Report Form to the Sponsor within 24 hours of the initial call or e-mail and follow-up with CRF submission within 3 working days of identification. When faxing the notification and supporting documentation, the SAE Report should be included. Refer to the Personnel and Facilities section for Sponsor contact information for reporting of SAEs and Serious Adverse Device Effects. Sites must also report these events to the reviewing EC/IRB per their established reporting procedures.

2. Off-Site Serious Adverse Event (SAE) Reports

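### The protocol's only causality scale rates one merged, undefined object (study device/study protocol), so it cannot give the relationship to the Zepto system that Section X.B asks for

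*Protocol*

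**What the plan says.** Three places in Section X say what an adverse event's relationship is to be judged against, and they differ.

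- **X.B, Identification and Collection:** the investigator will "assess its relationship to the Zepto™ system and the severity of the event (see definitions provided below"). The object is the Zepto system alone, and the reader is sent on to X.C for the grades.
- **X.C, lead-in:** the investigator must assess "the relationship of the event to the study device and study procedure".
- **X.C.2, the grades:** *Probably* is for an event "which might have a direct relationship to the study device/study protocol". *Unrelated* is for an event "which has no direct or indirect relationship to the study device/study protocol". *Possibly* and *Unlikely* use the same pair.

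The protocol does not define study procedure or study protocol for this purpose. Section VII says that every study eye has the Zepto capsulotomy "followed by conventional phacoemulsification and IOL implantation". Under *Unrelated*, X.C.2 accepts "effect of another procedure/device/drug" as an alternative cause.

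**The concern.** This is a single-arm device study, so no control group shows how much of the observed morbidity belongs to ordinary cataract surgery. X.B lists 21 kinds of event that must be documented and evaluated even though they may be normal after such surgery. Event-level attribution is therefore an important means of separating a device effect from a surgical one. If the scale merges the device with everything else the protocol requires, a *Probably* does not tell the reader that the device was involved.

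Device involvement matters elsewhere in the protocol. X.A defines adverse device effect, serious adverse device effect and unanticipated adverse device event by reference to the device. Section VI.B describes the primary safety endpoint as posterior capsular rupture and vitreous loss related to the Zepto capsulotomy, but has the surgeon record only Yes or No.

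**Working it through.** The point rests on the text, so the check is to apply the X.C.2 wording to test cases and then trace what depends on the answer.

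**Step 1: apply the scale.** IX.D describes the Zepto system as the disposable handpiece with its tip and the console. Suppose in each case that the cause is clear.

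| Cause of the event | Zepto system (X.B question) | Study device/study protocol (X.C.2 object) | X.C.2 grade |
|---|---|---|---|
| Zepto tip tears the capsule | Yes | Yes | *Probably* |
| Rhexis ruler tears the capsule | No | Yes: VI.C.3 and Appendix 3.G require the measurement | *Probably* |
| Phacoemulsification causes corneal edema | No | Not settled by the text | *Probably* or *Unrelated* |
| Cause outside surgery and study | No | No | *Unrelated* |

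The first two rows receive the same grade but have opposite answers to the X.B question. That is enough to show that the scale does not isolate the device, and it needs no view on phacoemulsification. The third row shows a further ambiguity: two investigators could reasonably grade the same event differently.

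**Step 2: trace what depends on device relationship.**

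- *ADE and serious ADE classification (X.A):* depends on the device. The X.C.2 grade does not supply it.
- *Non-serious ADE report (X.E, 10 working days):* applies only if the event is an ADE, so it is affected.
- *Serious events (X.E):* a serious adverse event and a serious ADE share one row, 24 hours and then 3 working days. Not affected.
- *Unanticipated events (X.E):* the device and non-device forms share one row, 24 hours and then 5 working days. Not affected.
- *Exit follow-up (X.F):* worded for device and procedures jointly. It does not need the two separated.
- *Primary safety endpoint (VI.B):* affected if the restriction to Zepto-related events is applied.

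**Step 3: how much attribution could matter for the safety endpoint.** Section XI.B plans on 4% of 100 eyes. The exact (Clopper-Pearson) limits for x events in n = 100 are

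lower = Beta quantile(0.025; x, n − x + 1), upper = Beta quantile(0.975; x + 1, n − x).

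For x = 4 this gives 1.10% to 9.93%, which reproduces the protocol's interval. Now assume that 4 ruptures occur and only some are attributed to Zepto:

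| Attributed to Zepto | Exact 95% interval |
|---|---|
| 4 | 1.10% to 9.93% |
| 3 | 0.62% to 8.52% |
| 2 | 0.24% to 7.04% |
| 1 | 0.03% to 5.45% |
| 0 | 0% to 3.62% |

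The number of ruptures and the split are assumptions. The table shows only that the reported rate and interval would depend on attribution.

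**The case against.** **The scale may be meant to exclude conventional surgery.** Section II calls cataract surgery with phacoemulsification the standard of care, and Section VII calls the phacoemulsification conventional. The procedure set out in IX.E ends with the capsulotomy. The first three grades elaborate the relationship only with device matters such as malfunction, deployment and labeling, and *Unrelated* allows another procedure as the cause. This stands as a plausible reading. A reader might infer from Section VII that phacoemulsification is definitely part of the study protocol, but the documents leave that open. The ruler case survives either way: its use is a measurement the protocol requires, so its effects cannot be without relationship to the study protocol.

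**There is only one scale.** A reader might infer that X.B and X.C are competing rules that put the same event at opposite ends of the scale. The text does not support that. X.B has no grades and defers to X.C. The defect is one scale whose object is wider than the question it is meant to answer.

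**The consequences are limited.** This stands in part. The clocks for serious and unanticipated events and the exit rules are unaffected. X.A defines an ADE on its own terms and does not tie it to a grade, so an investigator can still classify one, but without help from the scale. The analysis in Section XII tabulates adverse events by type and does not use the grade. Completeness, anterior capsule tear and corneal touch are recorded directly at the capsulotomy, and device malfunctions have their own report, so attribution is not the only evidence on the device.

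**The form may already have two boxes.** IX.G says that the case report forms are provided separately, so this is possible. The grade definitions that investigators would apply would still be merged. Variation between sites is a risk, not something the documents show.

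**Conclusion.** The point holds in a limited form. X.B asks about the Zepto system, the X.C lead-in about device and procedure, and all four grades about a merged and undefined object. The protocol's only causality scale therefore cannot isolate device relationship. The effect falls on ADE and serious ADE classification, on the 10-working-day report for a non-serious ADE, and on any attribution needed to apply the Zepto-related wording of the primary safety endpoint in VI.B.

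The number of events affected cannot be estimated from the protocol. For the safety endpoint, on the assumption of 4 ruptures in 100 eyes, the upper 95% limit could lie anywhere from 9.93% down to 3.62% depending on attribution. That range applies only if the endpoint is restricted to Zepto-related events. The rest of the conclusion needs only that the ruler is a protocol step and not part of the Zepto system, which IX.D, VI.C.3 and Appendix 3.G support.

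**What to change.** Reconcile X.B, the X.C lead-in and the four X.C.2 grades as follows.

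1. Rate each event twice on the existing four grades: (i) relationship to the Zepto device and capsulotomy step, and (ii) relationship to the other surgical or study procedures.
2. State that phacoemulsification and IOL implantation fall under (ii), together with other steps that are not Zepto, such as the rhexis ruler.
3. In each grade, replace the merged device/protocol wording with the object being rated.
4. Base ADE and serious ADE classification on rating (i). Since X.A counts user error and inadequate instructions as device effects, say that rating (i) covers them.
5. If the primary safety endpoint is to be limited to Zepto-related ruptures, say in VI.B that rating (i) decides it. If not, remove that restriction from VI.B.

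The cost is one extra field on the adverse event form, four edited definitions and short edits to X.B, the X.C lead-in and VI.B. No extra visits or measurements are needed.
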